6 MONTHS: ACTIVE TREATMENT GROUP ONLY

Following the final enrolled subject's completion of the Week 8 Post-Treatment Evaluation, study blinding will be broken. Subjects who had been assigned to the active treatment group will take part in the 6 months post-procedure evaluation visit to gain a sense of duration of the treatment effect. At this visit, the following study measures will be recorded:

- Aberrant Behavior Checklist (ABC)
- Clinical Global Impressions (CGI)
- Medication and therapy use review
- Adverse events evaluation

PLACEBO SUBJECTS POST-STUDY CROSS-OVER OPTION

Following study unblinding, subjects who had received the placebo device will be offered the opportunity to receive the same active course of treatment as was administered to subjects who had been assigned to the active device treatment group. Subjects who wish to engage in this option will re-commence the study at the study qualification evaluation phase. Given the nature of the condition, behavioral and functional change in either direction may be expected, and as such, study qualification and baseline evaluations will be redone for this cross-over subject group, with the exception of the DSM-IV-TR diagnosis confirmed with the ADI-R as both will be current within the past 2 years as per the study inclusion qualification criteria based upon the subject's initial enrollment on the study. Subjects will then proceed through the remainder of the course of the study as when they participated as a placebo subject and proceed to the post-procedure evaluation phase. Although these subjects and their caregivers will be aware that active treatment is being administered during this crossover phase, again by nature of the condition, the subjects are incapable of purposefully altering their behavior or function, so this will not impact the outcome of the placebo cross-over phase.

STATISTICAL ANALYSIS PLAN

The aim of this study is to determine if the treatment effect of the Erchonia® HLS laser device for the active treatment group is greater than that for the placebo treatment group.

The study will be considered a success if, using the Intent-To-Treat (ITT) Last Observation Carried Forward (LOCF) analysis, the primary endpoint is statistically significant at the 0.05 level.

PRIMARY EFFICACY OUTCOME MEASURE

The primary efficacy outcome measure in this study is the mean change from baseline to study endpoint (end of the four-week treatment period) in the Aberrant Behavior Checklist (ABC) Irritability Subscale score.

Study success will be established through the detection of a minimum mean difference of -8.5 points between test and placebo groups in the change in ABC Irritability Subscale score from baseline to study endpoint (end of treatment week 4) adjusted for the baseline ABC Irritability Subscale score. The -8.5-point mean difference between treatment groups is considered clinically relevant with a SD of 8.9, a two-sided test with 80% power and a 5% level of significance.

Null Hypothesis: There is no difference in the mean change in ABC Irritability Subscale score from baseline to study endpoint adjusted for the baseline ABC Irritability Subscale score between active treatment and placebo groups, to the effect of less than -8.5 points.

Alternative Hypothesis: There is a difference in the mean change in ABC Irritability Subscale score from baseline to study endpoint adjusted for the baseline ABC Irritability Subscale score between active treatment and placebo groups, to the effect of -8.5 points or greater.

Rationale for Primary Efficacy Outcome Measure

Determination, application and support of the detection of a mean difference of -8.5 points between test and placebo groups in the change in the ABC Irritability Subscale score from Baseline to study Endpoint adjusted for the baseline ABC Irritability Subscale score being considered clinically relevant is based on the results of the clinical study for Abilify® (aripiprazole) that resulted in FDA clearance of the drug for the same exact intended indication as in this proposed pivotal trial combined with the results of a feasibility study employing the Erchonia® HLS Laser Device with the same device output parameters and treatment administration protocol as proposed for the current pivotal study.

Abilify® (aripiprazole) Study: In the Abilify® study, the primary efficacy endpoint was the mean change from Baseline to Week 8 LOCF in the ABC Irritability Subscale score. There was a statistically significant difference between the treatment groups in favor of Abilify® (aripiprazole) in the adjusted mean change from Baseline to Week 8 LOCF (study Endpoint) in the ABC Irritability Subscale score of -7.9 (placebo -5.0, aripiprazole -12.9, difference -7.9, 95% CI (-11.7, -4.1), $p < 0.001$). It was concluded that this change demonstrated clinically relevant and statistically significant improvement compared with placebo on the primary efficacy endpoint in the adjusted mean change from Baseline on the ABC Irritability Subscale at Endpoint.

FDA independent analysis concluded that the results of the clinical trials showed that treatment with aripiprazole is efficacious in improving the symptoms of irritability in children and adolescents with autism, as demonstrated by the results on the primary endpoint, ABC Irritability Subscale. It was stated that **aripiprazole showed clinically meaningful and statistically significant improvement compared with placebo** through study Endpoint evaluation on the

primary efficacy measure of mean change from Baseline to Week 8 in the ABC Irritability Subscale score.

Erchonia® HLS Feasibility (Pilot) Study: A feasibility (pilot) study that employed the Erchonia® HLS Laser Device with the exact same device output parameters and treatment administration protocol as proposed for the current pivotal study was completed in September, 2012.

In the pilot study, eleven (9 male and 2 female) children and adolescents aged 5 years 4 months to 16 years 10 months with autistic disorder were enrolled according to the study qualification criteria proposed for the current pivotal clinical study. All subjects received the active procedure administrations with the actual Erchonia® HLS Laser Device. The Aberrant Behavior Checklist (ABC) assessment tool was administered at Baseline evaluation (before receiving the first laser treatment administration) and at study Endpoint (after completion of the laser treatment administration protocol).

For subjects enrolled in this pilot study, the mean change from Baseline to study Endpoint in the Aberrant Behavior Checklist (ABC) Irritability Subscale score adjusted for Baseline ABC Irritability Subscale score was -9.09 (SD of change of 6.76). The mean Baseline ABC Irritability Subscale score was 14.45 (SD of 8.18) and the mean study Endpoint ABC Irritability Subscale score was 5.36 (SD of 6.70).

ANCOVA analysis for two correlated samples to evaluate the mean change from Baseline to study Endpoint in the Aberrant Behavior Checklist (ABC) Irritability Subscale score adjusted for Baseline ABC Irritability Subscale score found the mean change of -9.09 to be statistically significant at $p < 0.0005$ ($F = 23.27$; $p = 0.00012$).

Subsequently, based on the clinically significant results from the Abilify® clinical trial combined with the pilot study results from the Erchonia® HLS study demonstrating the predicted effect size of the Erchonia® HLS Laser Device and associated treatment administration protocol for the proposed indication, the midpoint in the change on the ABC Irritability Subscale score is determined to be -8.5 points, and the clinically significant study success for the currently proposed full-scale clinical study is defined as a minimum mean difference of -8.5 points on the ABC Irritability Subscale score from Baseline to Endpoint between active and placebo treatment groups.

Therefore, the estimated clinically significant effect size of the Erchonia® HLS Laser Device as applied to children and adolescents with autistic disorder in the proposed clinical study based on prior experience and research is a minimum mean difference of -8.5 points on the ABC Irritability Subscale score from baseline to endpoint (week four) between active and placebo treatment groups.

SECONDARY EFFICACY OUTCOME MEASURES

The following secondary efficacy outcome measures will be evaluated in this study:

- *Positive Response Rate*: Difference in Positive Response Rate between treatment groups, where 'Positive Response Rate' is defined as satisfaction of both of the following 2 criteria:
 - ✓ $\geq 25\%$ reduction from baseline to endpoint in the Aberrant Behavior Checklist (ABC) Irritability Subscale score based on the subject's primary caregiver's rating; AND
 - ✓ Clinical Global Impressions – Improvement (CGI-I) scale rating of 1 or 2 (much improved or very much improved) at study endpoint as determined by the clinician's evaluation
- Mean change from baseline to endpoint in the other 4 ABC Subscale scores, based on ratings by the subject's primary caregiver:
 - ✓ Lethargy/Social Withdrawal
 - ✓ Stereotypic Behavior
 - ✓ Hyperactivity/Noncompliance
 - ✓ Inappropriate Speech
- Mean change from baseline to endpoint in the global ABC score
- Change in ratings on the CGI-S from baseline to study endpoint evaluation
- Change in ratings on the CGI-I from baseline to study endpoint evaluation

STATISTICAL METHODS

Efficacy analysis will be according to the intent to treat (ITT) principle by last observation carried forward (LOCF).

Intent to Treat: Subjects will be included in the ITT analysis if they complete their baseline clinical assessments and had at least one post-randomization efficacy evaluation and corresponding baseline value.

Last observation carried forward (LOCF): Missing data will be handled by carrying forward the last observation for the relevant measure. The LOCF data set included data recorded at a given time point, or, if no observation was recorded at that time point, data carried forward from the previous time point with available data. Baseline data will not be carried forward or averaged to impute missing values for the LOCF data set.

STATISTICAL ANALYSIS

Primary Efficacy Analysis

For the continuous primary efficacy measure of ABC Irritability Subscale score, change scores will be evaluated by analysis of covariance (ANCOVA). The ANCOVA models for LOCF data sets will include the baseline measure as a covariate and treatment (active of placebo) as main effects.

Secondary Measures Analysis

- For the continuous secondary efficacy measures of the other 4 ABC Subscale scores, and the Global Score, change scores will be evaluated by analysis of covariance (ANCOVA). The ANCOVA models for LOCF data sets will include the baseline measure as a covariate and treatment (active of placebo) as main effects. A two-way significance level of 5% will be considered to be statistically significant.

- For the categorical measures of the CGI will be analyzed within the framework of the generalized Cochran-Mantel Haenszel (CMH) procedure.
- Responder rate will be evaluated using Fisher's exact test to compare the proportion of responder rates between the test and control groups.

P-values will be 2-tailed tests of significance rounded to 3 decimal places. All analyses will be performed at the 5% significance level.

SAFETY ANALYSES

Safety analyses will be completed on all subjects who were randomized to treatment group and received at least the first study treatment administration with the Erchonia® HLS Laser device.

Safety will be assessed by evaluating and comparing frequency and incidence of observed and/or reported adverse events between test and placebo treatment groups. A chi-square test with a continuity correction will be performed to compare the percentage of subjects who had adverse events and/or reactions between the test and placebo group subjects.

SAFETY AND CONFIDENTIALITY ISSUES

ADVERSE EVENTS

At any time throughout the study, any adverse event reported by a subject and/or subject's caregiver and/or observed by the study investigator will be recorded on the case report form and subsequently evaluated by the Principal Investigator for its relation to the study treatment and whether or not any corrective action need be taken. All applicable adverse events will be reported to the IRB.

Formal evaluation of the occurrence of any adverse events will take place at the end of each study treatment administration and each evaluation visit. In addition, subjects/caregivers will be instructed to contact the investigator at any other time that he or she believes a potential adverse event has occurred during the course of the subject's participation in the clinical study.

The investigator will record the observation or report of any adverse event and assign the relationship to the study treatment on the appropriate case report form in the subject's file and will report the occurrence to the governing IRB, if and as appropriate, within 5 days of the reported occurrence, or within 24 hours in the occurrence of a serious adverse event including death.

The only known potential adverse event associated with the use of laser devices is that long-term exposure to laser light could cause damage to eyesight. As a precaution, during all laser treatment administrations with the Erchonia® HLS at the test site, both the subject and the administration investigator will wear safety glasses that filter out the laser light spectrum. The administration investigator will wear KenTek Corporation KenTek C22-KMT-6101 light blue safety glasses and the subject will wear KenTek Corporation KGOG-6101 light blue Medium Goggles safety goggles. Additional information on this safety eyewear is contained above on pages 6-8 under the section titled: DEVICE SAFETY: RISK AND PREVENTION OF EYE INJURY.

There are no other known potential adverse events from application of the study lasers. There have been no observed or reported adverse events or reactions to the application of the family of Erchonia® laser devices in several other studies using these laser devices. However, potential adverse events that may occur include, but are not necessarily limited to: skin irritation, skin discoloring, skin rash, skin indentations and infection. There may also be unknown or unanticipated risks to using the laser devices with this study treatment.

MONITORING OF THE CLINICAL STUDY

The study Monitor will assure that the investigator is executing the protocol as outlined and intended. This includes insuring that a signed informed consent form has been attained from each subject's caregiver prior to commencing the protocol, that the study procedure protocol is administered as specified, and that all study evaluations and measurements are taken using the specified methods and correctly and fully recorded on the appropriate clinical case report forms.

SUBJECT PRIVACY AND CONFIDENTIALITY

Records for each subject in the study will be maintained in separate files in a locked filing cabinet at the test site. The Principal Investigator will be responsible for ensuring that all records for a subject are stored in that subject's file at all times other than when information is being recorded on them.

Once a subject's participation in the study is complete and all of the required records are in the subject's file, copies of the documents may be made and supplied to the study Sponsor who will store them in a locked filing cabinet. Copies of subjects' case report forms will also be sent to Regulatory Insight, Inc. for the purpose of monitoring the data collection process and analysis of results. Regulatory Insight, Inc. will also maintain these copies in a separate clinical study file that is kept in a locked filing cabinet. The original records will be maintained at the test sites upon completion of the study in their original files and stored in a locked filing cabinet.

Subjects' identities will be kept confidential by assigning each subject a subject ID upon acceptance into the study. The subject ID will comprise the investigator's first and last name initials and a three-digit number that will be determined based upon the subject's order of entry into the study. For example, the eighth subject to be enrolled under Principal Investigator [name] will have a subject ID of MB008. Neither the study Sponsor nor Regulatory Insight, Inc. will receive any additional identifying information about a subject and will therefore have no way of linking a subject ID to a particular subject and his or her results.

INFORMED CONSENT

- Informed consent will be an agreement between the study PI and each subject's designated caregiver, having the capacity to understand and make an informed decision. Consent will be obtained prior to each potential subject's participation in this clinical trial.
- The caregiver for each subject participating in this clinical trial will be made aware of the fact that the subject's participation involves research and the intent of the research, the expected duration of participation and a description of the procedures that will be followed.
- The caregiver for each subject will be made aware of the reasonably expected benefits the subject might receive, as well as any risks or potential discomfort that are involved.
- The caregiver for each subject will be made aware of alternative procedures that are available to the subject.
- The caregiver for each subject will be made aware that the subject's records will remain confidential, but that the FDA and the IRB has the right to inspect those records.
- The caregiver for each subject will be told that the subject's participation in the clinical trial is voluntary, without force or influence from the investigator or sponsor.
- The caregiver for each subject will be given the name and method of contacting the appropriate person(s) to answer any questions about the research and in the event of research-related injury.

The informed consent form can be found in **Appendix B**.

CASE REPORT FORMS

The case report forms that will be used to collect the data from each subject in this clinical trial can be found in **Appendix C**.

TABLE OF SUBJECT EVENTS

The following table provides a progressive summary of subject events throughout the duration of this pivotal trial.

PRE-TREATMENT ACTIVITIES
STUDY QUALIFICATION

 ➤ A minor individual who attends the investigator’s office for a pre-scheduled appointment pertaining to his or her ASD and/or ASD-related issues is deemed potentially suitable by the investigator for participation in the clinical study. ➤ The investigator discusses the possibility of participating in the study with the caregiver. ➤ If the caregiver is interested, the investigator presents and reviews the study informed consent form with the caregiver and reviews the information sheet with the child/adolescent. ➤ The caregiver voluntarily signs the study consent form. ➤ Subject ID is assigned. ➤ Subject is randomly assigned to Treatment Group. ➤ Study qualification inclusion/exclusion criteria evaluation is performed.
BASELINE ASSESSMENT

DEMOGRAPHICS AND TREATMENT HISTORY
 
 ➤ Demographic Variables recorded: gender, age, ethnicity ➤ Medication and Treatment History: Recording of all prescription and OTC medications used to date and therapies tried to date to treat autistic disorder or for any other indication 
BASELINE EVALUATION
 
 ➤ Aberrant Behavior Checklist (ABC) ➤ Clinical Global Impressions (CGI) Severity of Illness Scale (CGI-S) only
PROCEDURE ADMINISTRATION PHASE

GENERAL ASSESSMENT CONDITIONS
 
 ➤ Subject agrees to maintain his or her regular medication and dosage schedule to treat symptoms related to autism disorder throughout the study. ➤ Subject agrees to not change or start taking any new medications, or partake in any other new treatments, or to change the dosages they take of current medications, to treat the symptoms of autism disorder, during the course of study participation ➤ Subject agrees to notify the study investigator immediately if their treating physician makes any change to medication or dosage. ➤ Females of child-bearing age agree to use acceptable means of contraception throughout the study.

STUDY TREATMENT ADMINISTRATION PROTOCOL

The subject receives eight 5-minute study treatments with the Erchonia® HLS laser device: two treatments per week for 4 consecutive weeks, each treatment administration 3 to 4 days apart administered by the study investigator at the test site.

TREATMENT ADMINISTRATION PHASE: 4 WEEKS

AT EACH OF THE 8 STUDY TREATMENT ADMINISTRATION VISITS

- Medication and therapy use review
- Adverse events evaluation

WEEK 2 END: Study Midpoint

- Aberrant Behavior Checklist (ABC)
- Clinical Global Impressions (CGI)

WEEK 4 END: Study Endpoint

- Aberrant Behavior Checklist (ABC)
- Clinical Global Impressions (CGI)

POST-TREATMENT EVALUATION PHASE

WEEK 8: Four weeks following completion of the Treatment Administration Phase:

- Aberrant Behavior Checklist (ABC)
- Clinical Global Impressions (CGI)
- Medication and therapy use review
- Adverse events evaluation

6 MONTHS: For Active Treatment Subjects Only

- Aberrant Behavior Checklist (ABC)
- Clinical Global Impressions (CGI)
- Medication and therapy use review
- Adverse events evaluation

PLACEBO SUBJECTS POST-STUDY CROSS-OVER OPTION

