5. An individual for whom the caregiver decides not to permit participation in the study will continue to work with the physician on the ASD treatment plan goals for the minor patient.

Compensation

A subject or his or her caregiver(s) will not be offered money or any other form of compensation to participate in the clinical study; however, there will also not be any charge for the cost of the study treatments with the Erchonia® HLS laser device or for the cost of any other directly-related evaluations or measurements that occur as part of the subject's participation in this study.

Subject Sample Size

There will be 40 qualified subjects enrolled in this clinical study:

- 20 subjects in the test group
- 20 subjects in the control group

Rationale and Justification for Sample Size

This study is powered to compare one active arm with placebo. Sample size calculation is based on the primary efficacy measure of the mean change from study baseline to endpoint (end of the 4-week treatment period) in the Aberrant Behavior Checklist (ABC) Irritability Subscale score adjusted for the baseline ABC Irritability Subscale score.

Based on detecting a mean difference of -8.5 points between test and placebo groups in the change in ABC Irritability Subscale score adjusted for the baseline ABC Irritability Subscale score being considered clinically relevant with a SD of 8.9, a two-sided test with 80% power and a 5% level of significance, the number of subjects needed per treatment group is 18.

From here, it is anticipated that about one-tenth of subjects overall may withdraw or be terminated from the study prior to completion for various reasons. Therefore, the following formula is used to determine the final needed starting sample size for each procedure arm:

Final sample size = sample size X $1/(1-d)$; where $d = \# \text{ expected dropouts}/\# \text{ subjects enrolled}$.

Final sample size = $18 \times 1/(1-0.11)$; where $d = 2/19$

Final sample size = $18 \times 1/0.89 = 18 \times 1.124 = 20$ subjects per treatment group.

Therefore, a minimum starting sample size of 20 subjects in each treatment group (40 subjects in total) is needed to ensure that a sufficient number remains at study endpoint (18 evaluable subjects per treatment group) for any significant differences found between treatment groups to be considered statistically valid and representative of the general population being sampled.

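### Study success is defined both as p < 0.05 and as a minimum difference of -8.5 points; at the planned effect of -8.5 the second rule has at most 50% power, not 80%

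*Combined protocol and SAP*

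**What the plan says.** The combined protocol and SAP states the criterion for success in three places.

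- **Statistical Analysis Plan, opening paragraphs.** The study succeeds if, in the ITT analysis with LOCF, "the primary endpoint is statistically significant at the 0.05 level". No minimum difference is attached.
- **Primary Efficacy Outcome Measure.** "Study success will be established through the detection of a minimum mean difference of -8.5 points between test and placebo groups". The null hypothesis says there is no difference "between active treatment and placebo groups, to the effect of less than -8.5 points", and the alternative that there is one "between active treatment and placebo groups, to the effect of -8.5 points or greater".
- **Rationale for Primary Efficacy Outcome Measure.** "the clinically significant study success for the currently proposed full-scale clinical study is defined as a minimum mean difference of -8.5 points".

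Two further sections bear on the point. Rationale and Justification for Sample Size uses the same number as the assumed effect: "Based on detecting a mean difference of -8.5 points between test and placebo groups in the change in ABC Irritability Subscale score". With an SD of 8.9 it concludes, for "a two-sided test with 80% power and a 5% level of significance, the number of subjects needed per treatment group is 18". The Primary Efficacy Analysis section plans an ordinary ANCOVA of change scores with baseline and treatment in the model, and all analyses are at the 5% level. No test against -8.5 is described.

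**The concern.** One number is doing two jobs. As the effect assumed in the power calculation, -8.5 is the centre of the distribution of results the sponsor expects. As a pass mark, it is the value a result must reach. An estimate centred on its own pass mark reaches it half the time, so 80% power cannot hold for that rule at that effect.

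The trial is pivotal and meant to support a de novo application. A statistically significant result short of -8.5 would be a success by the opening of the analysis plan and a failure by the sections that follow. The verdict could then be chosen after the data are seen.

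The hurdle also sits awkwardly with its own rationale. The plan cites a placebo-adjusted drug effect of -7.9 as clinically relevant, yet an observed -7.9 in this trial would fail the -8.5 rule.

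**Working it through.** **Inputs.** From Rationale and Justification for Sample Size: difference 8.5, SD 8.9, two-sided 5%, 80% power, 18 evaluable and 20 enrolled per arm. From the primary outcome rationale: drug-trial difference -7.9 and pilot change -9.09. Differences are written below as magnitudes in favour of the device.

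**1. Reproduce the plan's figure.** Against a null of zero, n per arm = 2 × (1.96 + 0.842)² × (8.9/8.5)² = 17.2, rounded up to 18. The stated figure is reproduced. Noncentral-t power is 79.5% at 18 per arm and 83.7% at 20. A one-sided test would need only 14, so the plan's 18 is a two-sided test of zero difference with 8.5 as the assumed true effect.

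**2. Smallest significant observed difference.** SE = 8.9 × √(2/n).

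- n = 18: SE = 2.967; 2.032 × 2.967 = 6.03
- n = 20: SE = 2.814; 2.024 × 2.814 = 5.70

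**3. Observed difference must reach 8.5.** P(success) = Φ((true − 8.5)/SE), here with n = 18.

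- True 8.5: Φ(0) = 50%, for any SD or n
- True 7.9: Φ(−0.6/2.967) = 42%
- True 9.09: Φ(0.59/2.967) = 58%
- For 80%, the true difference must be 8.5 + 0.842 × 2.967 = 11.0 (10.9 with n = 20)

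Requiring p < 0.05 as well leaves the 50% unchanged (100,000 simulated trials), because at this SD and n an observed 8.5 is practically always significant.

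**4. Hypotheses read literally, with 8.5 as the null boundary.** P(success) = Φ((true − 8.5)/SE − 1.96).

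- True 8.5: Φ(−1.96) = 2.5%, which is the type I error rate
- For 80%, the true difference must be 8.5 + 2.80 × 2.967 = 16.8 (16.4 with n = 20)

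**5. Zone where the rules disagree, at a true difference of 8.5.** This is P(significant) minus P(observed at least 8.5).

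- n = 18: 79.5% − 50% = about 30%, for observed differences from 6.0 to 8.5
- n = 20: 83.7% − 50% = about 34%, for observed differences from 5.7 to 8.5

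| Rule | P(success) at true 8.5, n = 18 | n = 20 | True difference for 80%, n = 18 |
|---|---|---|---|
| p < 0.05 against zero | 79.5% | 83.7% | about 8.5 |
| Observed difference at least 8.5 | 50% | 50% | 11.0 |
| Test with null at 8.5 | 2.5% | 2.5% | 16.8 |

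**The case against.** The best defence is that -8.5 was only ever the design effect. The sentence after the success statement uses sample-size language (SD, power, significance level), and the rationale ends by calling -8.5 an estimated effect size. The rationale's definition also speaks of clinically significant success, which could sit beside statistical success rather than replace it. This reading is plausible and probably close to the intent. It does not remove the conflict: the text expressly makes -8.5 the definition of study success, builds both hypotheses on it, and never says how the two criteria combine.

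Four narrower points stand as qualifications.

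- The 50% ceiling applies when the true effect is -8.5 or smaller. A larger true effect gives more. But -8.5 is the effect to which the stated 80% is tied.
- No section plans a test against -8.5. The 2.5% figure shows what the written hypotheses imply, not an analysis anyone scheduled.
- The rules are nested at the planning SD and n: a result of -8.5 or beyond passes both. They disagree only in the zone worked out above.
- A sponsor may set a hurdle above a comparator drug's effect. Failing an observed -7.9 is not an error in itself; it only shows that the hurdle was not reconciled with its rationale.

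**Conclusion.** The concern holds. The plan gives two success rules that can return opposite verdicts, and the stated 80% power belongs only to the significance rule. At the planning effect of -8.5, the minimum-difference rule has a 50% chance of success as an observed threshold, and 2.5% if the hypotheses are taken as a margin test. The 50% and 2.5% do not depend on the SD or the sample size. The limits of the disagreement zone and its 30% to 34% probability assume that the SD of 8.9 applies to the baseline-adjusted comparison, with 18 to 20 analysed per arm. The sample size is sound for a test against zero. What is wrong is the definition of success around it, and it must be fixed because the pivotal verdict is otherwise undefined.

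**What to change.** State one success rule, and settle it before unblinding. The rule that matches the planned ANCOVA and the sample size is the significance rule.

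- Write H0: adjusted mean difference = 0 against H1: adjusted mean difference ≠ 0, with success requiring two-sided p < 0.05 in the direction favouring the device.
- Remove the minimum difference of -8.5 as a success condition from Primary Efficacy Outcome Measure and its Rationale. Describe it only as the planning effect.
- Report the adjusted difference with its 95% CI, so that clinical relevance can be judged from the estimate.

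This changes wording only and needs no extra subjects or data.

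If the sponsor wants to keep -8.5 as a hurdle, the plan must say whether it applies to the point estimate or to the confidence limit. It must also either restate the power at -8.5 (50% or 2.5%) or recompute the sample size under a larger assumed true effect. That route is not free. For the point-estimate rule, n per arm = 2 × (0.842 × 8.9/(true − 8.5))². Taking the pilot's uncontrolled 9.09 as the true difference, purely for illustration, gives 2 × (7.49/0.59)², or about 323 per arm.
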